2. SYNOPSIS

Study Title	FROSTTIE: A randomised controlled trial of FRenotomy and breastfeeding support Or breastfeeding Support without frenotomy to investigate continuation of breastfeeding for babies with Tongue-TIE		
Internal ref. no. / short title	FROSTTIE		
Study Design	Multicentre randomised controlled trial		
Study Participants	Any baby aged up to ten weeks refer breastfeeding difficulties and judged to		
Planned Sample Size	870		
Planned Study Period	Participant involvement for 36 months; of intervention collecting routine health		
Aim	To investigate whether frenotomy is clinically and cost effective to promote continuation of breastfeeding at three months in infants with breastfeeding difficulties diagnosed with tongue-tie.		
	Objectives	Outcome Measures	
Primary	To compare the rate of any breastfeeding at 3 months of age in infants with breastfeeding difficulties and diagnosed tongue-tie who undergo frenotomy and receive breastfeeding support versus those who receive breastfeeding support only.	Any breastmilk feeding at 3 months according to maternal self-report, defined as any breastmilk feeding in the 24 hours prior to the infant reaching three months of age. A positive response is indicative of continuation of breastfeeding.	
Secondary	To investigate the effect of frenotomy on various important other secondary outcomes measured at first follow-up visit and/or three months of age. To investigate the impact of tonguetie severity and mothers' prior beliefs on the primary outcome.	Measured at first follow-up visit and 3 months of age: • mother's pain while feeding during the previous 24 hours • exclusive breastmilk feeding • exclusive direct breastfeeding • frenotomy in comparator group • repeat frenotomy • bleeding (following frenotomy or frenulum tear) • post-procedure adverse events (tongue cut, scarring, salivary duct damage)	

maternal anxiety and depression dimension of EQ-5D-5L
 maternal health-related quality of life (EQ-5D-5L)
 Measured at 3 months of age:
 mother's breastfeeding self-efficacy (Breastfeeding Self-Efficacy Scale – Short Form)
 amount of breastfeeding support

- used, measured by total number of contacts with any breastfeeding supporter since the FROSTTIE procedure (whether face to face, or by telephone)
- infant weight gain from birth
- infant post-randomisation weight gain
- age of child when s/he last received breastmilk
- time spent breastfeeding in previous 24 hours
- maternal health-related quality of life (EQ-5D-5L)
- maternal and infant NHS healthcare resource use
- To examine, through an alongside economic evaluation, whether any additional benefits associated with frenotomy are justified by any additional health care resources needed to deliver the intervention
- To investigate the effect of frenotomy on breastfeeding rates measured at six months.

Secondary outcome measured at 6 months:

· any breastmilk feeding

3. TRIAL FLOW CHART

FROSTTIE Flow Diagram

Inclusion criteria

Any infant aged up to 10 weeks referred (by mother or other breastfeeding support service) to an infant feeding service with breastfeeding difficulties and judged to have tongue-tie

Exclusion criteria

Infants

- born at <34 weeks
- who have breastfeeding difficulties but are not judged to have tongue-tie
- with a congenital anomaly known to interfere with breastfeeding e.g. cleft palate, Down syndrome
- with a known bleeding diathesis
- who have had a frenotomy prior to recruitment

Randomisation

1:1 allocation ratio

Frenotomy with breastfeeding support

Frenotomy will be carried out by the usual trained practitioner for participating hospitals using their usual technique. Breastfeeding support will be at least the minimum specified level of support provided by participating hospitals

Breastfeeding support

Breastfeeding support will be at least the minimum specified level of support provided by participating hospitals

Primary Outcome

OR

Any breastmilk feeding at 3 months according to maternal self-report

Defined as any breastmilk feeding in the 24 hours prior to the infant reaching 3 months of age. A positive response is indicative of continuation of breastfeeding

Secondary outcomes

(measured at three months of age unless otherwise stated)

- Mother's breastfeeding self-efficacy
- Mother's pain while feeding during the previous 24h1
- Amount of breastfeeding support used
- · Infant weight gain and post-randomisation weight gain
- Exclusive breastmilk feeding: exclusive breastmilk feeding in the previous 24h³
- Exclusive direct breastfeeding: exclusive breastfeeding with no bottle feeds of expressed milk in the previous 24h¹
- Age of child when he/she last received breastmilk
- Time spent breastfeeding in previous 24h
- Frenotomy in comparator group/repeat frenotomy/bleeding following frenotomy or frenulum tear/ post-surgery adverse events (tongue cut, scarring, salivary duct damage)¹
- Maternal anxiety and depression dimension of EQ-5D-5L¹
- Maternal health-related quality of life1
- Maternal and infant NHS healthcare resource use
- Any breastmilk feeding according to maternal self-report²
- 1 at first follow-up visit also
- 2 at 6 months of age only

4. ABBREVIATIONS

BTAT	Bristol Tongue Assessment Tool
CI	Chief Investigator
CIG	Co-Investigator Group
CRF	Case Report Form
СТИ	Clinical Trials Unit
DMC	Data Monitoring Committee
HRA	Health Research Authority
LATCH	A breastfeeding assessment tool (Latch, Audible swallowing, Type of nipple, Comfort, Hold)
NHS	National Health Service
NICE	National Institute for Health and Care Excellence
NPEU	National Perinatal Epidemiology Unit
PI	Principal Investigator
PIL	Parent Information Leaflet
PMG	Project Management Group
RCT	Randomised Controlled Trial
REC	Research Ethics Committee
S/AE	Serious / Adverse Event
SF-MPQ	Short Form McGill Pain Questionnaire
SOP	Standard Operating Procedure
TSC	Trial Steering Committee

5. BACKGROUND AND RATIONALE

Tongue-tie can be diagnosed in 3–11% of babies (Edmunds et al. 2011), with the variation in reported prevalence thought to relate to the use of different diagnostic or severity criteria (Fox et al. 2016). However, less than 50% of babies with tongue-tie are reported to have breastfeeding difficulties, although this reported proportion is also highly variable, with some studies reporting almost universal difficulties, and others reporting very few feeding difficulties which relate to the tongue-tie itself, instead noting that incorrect positioning and attachment are the primary reasons behind the observed breastfeeding difficulties and not the tongue-tie itself (Edmunds et al. 2011). In a recent survey (Fox et al. 2016), it was noted that management of tongue-tie in infants with breastfeeding difficulties is therefore highly variable across the UK. This is coupled with highly variable provision of breastfeeding support (World Breastfeeding Trends Initiative 2016), which can range from minimal to expert and intensive, and using a variety of different models including peer supporter, midwife and health visitor.

A recent Cochrane review (O'Shea et al. 2017) has identified five prior RCTs of frenotomy including a total of only 302 infants. The trials are small and under-powered and/or include only very short-term or subjective outcomes, suggesting further robust evidence is needed. Hence there is considerable controversy regarding, not only the diagnosis and clinical significance, but also the management of tonguetie. Current NICE guidance (NICE 2005) allows for the procedure, based on lack of safety concerns, but notes very limited evidence of efficacy. There is therefore a clear need for an assessment of the clinical and cost-effectiveness of frenotomy for babies diagnosed with tongue-tie in the form of an adequately powered, pragmatic randomised controlled trial; taking into account the diagnostic controversy and variation in practice.

We therefore propose a multicentre randomised controlled trial, with internal pilot, to investigate whether frenotomy with breastfeeding support is clinically and cost-effective to promote continuation of breastfeeding at three months of age in infants with breastfeeding difficulties and diagnosed tongue-tie, compared with breastfeeding support only. Any baby aged up to ten weeks referred (by mother or other breastfeeding support service) to an infant feeding service with breastfeeding difficulties and judged to have tongue-tie will be eligible. The results of the trial will be generalisable to any population with a similar profile to those participating in the trial due to the pragmatic nature of the trial recruitment and intervention strategies.

6. OBJECTIVES AND OUTCOME MEASURES

Objectives	Outcome Measures	Time point(s) of evaluation of this outcome measure (if applicable)
Primary Objective To compare the rate of any breastfeeding at 3 months of age in infants with breastfeeding difficulties and diagnosed tonguetie who undergo frenotomy and receive breastfeeding support versus those who receive breastfeeding support only.	Any breastmilk feeding at 3 months according to maternal self-report: defined as any breastmilk feeding in the 24 hours prior to the infant reaching three months of age (Dennis, Jackson et al. 2014, McFadden, Gavine et al. 2017). A positive response is indicative of continuation of breastfeeding.	3 months of age
Secondary Objectives To investigate the effect of frenotomy on various important other secondary outcomes measured at first follow-up visit and/or three months of age. To investigate the impact of tonguetie severity and mothers' prior beliefs on the primary outcome.	Mother's breastfeeding self-efficacy: measured using the Breastfeeding Self- Efficacy Scale – Short Form Mother's pain while feeding during the previous 24 hours*: measured using visual analogue scale of the Short Form McGill Pain Questionnaire (SF-MPQ), modified into a Likert-type scale	First follow-up visit (outcomes indicated by *) 3 months of age (all secondary outcomes)
	Amount of breastfeeding support used: measured by total number of contacts (whether face to face or by telephone) with any breastfeeding supporter since the FROSTTIE procedure Infant weight gain: measured as difference in weight for age z-scores between birth and three months of age Infant post-randomisation weight gain: measured as difference in weight for age z-scores between baseline and three months of age	

Exclusive breastmilk feeding*: exclusive breastmilk feeding in the previous 24 hours

Exclusive direct breastfeeding*: exclusive breastfeeding directly from the breast with no bottle feeds of expressed milk in the previous 24 hours

Age of child when s/he last received breastmilk: age when child last received breastmilk, to determine when and whether switch to exclusive formula feeding has occurred

Time spent breastfeeding in previous 24 hours: time in minutes/hours spent breastfeeding in previous 24 hours

Frenotomy in comparator group*: measured by a specific question

Repeat frenotomy*: measured by a specific question

Bleeding following frenotomy or frenulum tear*: measured by a specific question

Post-procedure adverse events (tongue cut*, scarring, salivary duct damage*): measured by specific questions

Maternal anxiety and depression dimension of EQ-5D-5L*

Maternal health-related quality of life: as elicited by the EQ-5D-5L*

To examine, through an alongside economic evaluation, whether any additional benefits associated with frenotomy are justified by any additional health care resources needed to deliver the intervention

Maternal and infant NHS healthcare resource use: collected at 3 months of age on general practice visits and hospital admissions

To investigate the effect of	Any breastmilk feeding at 6 months	At 6 months of age
frenotomy on breastfeeding rates	according to maternal self-report: defined	
measured at six months.	as any breastmilk feeding in the 24 hours	
	prior to the infant reaching six months of	
	age	

7. STUDY DESIGN

A multicentre randomised controlled trial of frenotomy with breastfeeding support versus breastfeeding support with no frenotomy to investigate continuation of breastfeeding.

Infants aged up to ten weeks referred to an infant feeding service with breastfeeding difficulties and judged to have tongue-tie will be randomised to frenotomy with breastfeeding support versus breastfeeding support with no frenotomy.

The trial aims to recruit 870 participants from 19 centres in the UK over 24 months (2 recruits per centre per month). Each participant will undergo: screening/baseline, randomisation, intervention, routine post-intervention follow-up visit, 3 and 6 month post-intervention follow-up.

Data on the primary and secondary outcomes will be collected by mother's self-report via SMS text or web-link to data capture platform, or extracted from hospital records by assessors blinded to treatment allocation, or by linkage to routine data, where possible, for longer-term outcomes.

A training programme will be developed for recruiting midwives at all centres, to include consent processes, explanation of need for rapid access to breastfeeding support following group allocation to ensure mothers have high quality breastfeeding support and to minimise recourse to private frenotomy in the comparator group, tongue assessment using the Bristol Tongue Assessment Tool (BTAT) score (Ingram, Johnson et al. 2015) as well as standard trial processes.

In order to minimise bias, staff conducting follow-up visits should not be the same staff member who performed the procedure. All trial staff, with the exception of those providing the frenotomy service, will be masked to trial allocation wherever possible. Trial staff will be considered as follows in order to maintain masking as far as possible:

- Infant feeding/frenotomy service staff: Will conduct the initial assessment of infant eligibility and
 provide parents with information about the trial. Will take informed consent from parents who
 wish their infant to be entered into the trial. Infants randomised to the intervention will have the
 frenotomy performed without the parents directly observing the procedure; infants randomised
 to breastfeeding support alone will be shielded from view as if they were undergoing the
 procedure. Parents will thus be masked to allocation group. All parents will be provided with a
 standard post-frenotomy observed feed and standard post-frenotomy advice.
- Breastfeeding support workers: Follow-up breastfeeding support outside the hospital frenotomy clinic should be provided by different staff from those conducting the initial assessment of infants, and from those in the frenotomy service to maintain masking as far as possible. Support workers will be advised to urgently re-refer infants participating in the trial who have ongoing feeding difficulties to the hospital infant feeding service for further assessment in order to minimise the chance of parents seeking frenotomy with a private provider. Staff in the infant feeding service will offer breastfeeding support to any mothers referred back with the aim of avoiding frenotomy or repeat frenotomy. However, babies with ongoing problems may be re-referred to the frenotomy service for a first or repeat frenotomy in the event that this is felt to be clinically indicated.

7.1. Internal pilot

The internal pilot will assess monthly recruitment, masking, loss to follow up and contamination. It will assess the following assumptions:

- Monthly recruitment of 2 infants per centre by month 6
- Centres take 2 months to reach stable recruitment
- All pilot centres actively recruiting by month 6
- Masking is effective
- Loss to follow-up overall is less than 5%
- Contamination between arms is no more than 5%
- The proportion of babies recruited at four weeks or over is less than 40%

Pre-defined stop-go criteria after 9 months, with 266 recruits predicted, will be:

- Recruitment is 75% or more (N ≥ 199) continue directly with the main trial;
- Recruitment is 50-75% (133 ≤ N < 199) recruit more centres and review in 6 months;
- Recruitment is < 50% (N < 133) undertake an urgent detailed review of options with Trial Steering Committee to subsequently recommend to the funder.

All mothers of infants recruited during the pilot phase will be asked at the three-month follow-up whether they remained masked to their infant's treatment allocation. If parents remain masked, the study will continue with the masked design, recording blinding status.

8. PARTICIPANT IDENTIFICATION

8.1. Study participants

Infants aged up to 10 weeks referred to an infant feeding service (by a parent, midwife or other breastfeeding support service) with breastfeeding difficulties and judged to have tongue-tie.

Tongue-tie will be assessed using the BTAT; however all infants judged to have tongue-tie will be included irrespective of the formally assessed score.

Although not the study population, the mothers of eligible infants will be asked to consent for their babies and themselves to take part in the study as they will be providing outcome data, through maternal self-reporting, on their experiences amongst other measures.

8.2. Inclusion criteria

 Any infant aged less than 10 weeks referred (by parent or other breastfeeding support service) to an infant feeding service with breastfeeding difficulties and judged to have tongue-tie, whose parent has given informed consent for participation.

8.3. Exclusion criteria

Infants may not enter the study if ANY of the following apply:

- Infant is older than 10 weeks
- Infant has breastfeeding difficulties but is not judged to have tongue-tie
- Infant was born at less than 34 weeks' gestation
- Infant has a congenital anomaly known to interfere with breastfeeding e.g. cleft palate, Down syndrome
- Infant has a known bleeding diathesis
- Infant has had a frenotomy prior to recruitment

9. STUDY PROCEDURES

9.1. Recruitment

Potential participants will be identified by the infant feeding/frenotomy service staff from the population of infants with breastfeeding difficulties referred to hospital infant feeding services through volunteer breastfeeding supporters, other breastfeeding counsellors, midwives, or by self-referral by parents.

Parents will be provided with written and verbal information about the study. Any baby who is referred for tongue-tie will be screened for eligibility to take part.

9.2. Screening and eligibility assessment

As standard, following referral to hospital, infant feeding will be observed and tongue assessment conducted, and mothers will receive advice on positioning and attachment. To take account of the diagnostic controversy and varying opinions concerning clinical significance, any baby with breastfeeding difficulties diagnosed with tongue-tie is eligible for inclusion. The tongue-tie diagnosis will be made according to usual hospital practice which may include using any suitable tool. The degree of tongue-tie severity may vary, since there is no fully validated tool and no evidence associated with a specific cut-off in severity score. However, all babies whose parents consent for their participation in the trial will have an assessment of their tongue-tie made using the Bristol Tongue Assessment Tool (BTAT) (Ingram, Johnson et al. 2015), which will enable a subgroup analysis to examine the effect of frenotomy amongst babies who may be considered to have more and less severe tongue-tie.

9.3. Informed consent

A verbal explanation and written information, the Parent Information Leaflet (PIL), will be given to the parent(s). The parent(s) will be allowed as much time as they need to consider the information, and the opportunity to question staff to decide whether they consent for their baby to participate in the study. As the mother will be providing outcome data via self-reporting, they will also consent for themselves.

Written informed consent will then be obtained by means of the mother's dated signature and dated signature of the person who obtained the informed consent. The mother of the infant must personally sign and date the latest approved version of the informed consent form before any study specific procedures are performed.

Written informed consent will also include optional consent for linkage of their baby's data to routine data sources to allow the potential for further follow-up beyond the funded trial, for example to routine health visitor data at 2.5 years.

9.4. Randomisation

The infants entered into the trial will be randomised 1:1 to either:

- frenotomy with standard breastfeeding support (intervention arm), or
- no frenotomy with standard breastfeeding support (comparator arm).

Multiples (twins or higher order multiples) will be randomised to the same arm. Stratified block randomisation (using variable block sizes) will be performed via a secure 24-hour web-based randomisation system (hosted by the NPEU CTU, University of Oxford) stratified by infant's age (<2 and ≥2 weeks) at randomisation, mother's parity (primiparous or multiparous) within centre. A telephone back-up system will be available 24 hours a day (365 days per year). Users of the system will have no insight into the next allocation.

A statistician independent of the trial at the NPEU CTU will generate the randomisation schedule and the Senior Trials Programmer will write the web-based randomisation program; both will be independently validated. The implementation of the randomisation procedure will be monitored by the Senior Trials Programmer and independent statistician throughout the trial and reports will be provided to the Data Monitoring Committee.

9.5. Baseline assessments

Baseline information will be collected on sociodemographic and other characteristics, including:

- Infant birthweight
- Infant current weight
- Estimated date of delivery
- Current feeding practices (e.g. expressed breastfeeding, use of infant formula)
- Assessment of the degree of tongue-tie using the BTAT
- Mother's prior beliefs about frenotomy: Using a three-point Likert scale, the opinions of all
 mothers of infants recruited to the trial will be sought at the time of recruitment on their prior
 belief of the potential benefit of frenotomy
- EQ-5D-5L
- Mother's pain while feeding during the previous 24 hours: measured using visual analogue scale
 of the Short Form McGill Pain Questionnaire (SF-MPQ), modified into a Likert-type scale (scores
 ranging from 0 to 10) (Dennis, Jackson et al. 2014)
- Exclusive breastmilk feeding: exclusive breastmilk feeding in the previous 24 hours

• Exclusive direct breastfeeding: exclusive breastfeeding directly from the breast with no bottle feeds of expressed milk in the previous 24 hours

Pre-trial entry breastfeeding support received

9.6. Subsequent visits/data collection

9.6.1. Intervention

The following will be undertaken and data collected from the clinician performing the procedure on the day of the intervention:

- Intervention undertaken according to randomisation schedule and technique used (see section 9.4)
- · Bleeding following frenotomy or frenulum tear
- Post-procedure adverse events (tongue cut, salivary duct damage): measured by specific questions

9.6.2. Routine follow-up visit

The following data will be collected from the mother at the routine follow-up visit (approximately one week post-intervention according to hospital practice):

- Mother's pain while feeding during the previous 24 hours: measured using visual analogue scale
 of the Short Form McGill Pain Questionnaire (SF-MPQ), modified into a Likert-type scale (scores
 ranging from 0 to 10) (Dennis, Jackson et al. 2014)
- Exclusive breastmilk feeding in the previous 24 hours
- Exclusive breastfeeding directly from the breast with no bottle feeds of expressed milk in the previous 24 hours
- Request for frenotomy/repeat frenotomy (defined as any further procedure on tongue-tie)
- Bleeding following frenotomy or frenulum tear
- Post-procedure adverse events (tongue cut, salivary duct damage): measured by specific questions
- Maternal anxiety or depression as indicated by the anxiety and depression dimension of EQ-5D-5L
- Maternal health-related quality of life: as elicited by the EQ-5D-5L

9.6.3. 3 month follow-up

The following data will be collected using maternal self-report (by smart-phone, tablet, computer, postal questionnaire or telephone) when the infant is 3 months of age:

- Mother's breastfeeding self-efficacy: measured using the Breastfeeding Self-Efficacy Scale Short Form (Dennis 2003)
- Mother's pain while feeding during the previous 24 hours: measured using visual analogue scale
 of the Short Form McGill Pain Questionnaire (SF-MPQ), modified into a Likert-type scale (scores
 ranging from 0 to 10) (Dennis, Jackson et al. 2014)

 Total number of contacts with any breastfeeding supporter since first referral and specific means of support used

- Infant weight
- Exclusive breastmilk feeding in the previous 24 hours
- Exclusive breastfeeding directly from the breast with no bottle feeds of expressed milk in the previous 24 hours
- Age when child last received breastmilk, to determine when and whether switch to exclusive formula feeding has occurred (McAndrew, Thompson et al. 2010)
- Time spent breastfeeding in previous 24 hours: time in minutes/hours
- Request for frenotomy/repeat frenotomy
- Bleeding following frenotomy or frenulum tear
- Post-procedure adverse events (tongue cut, scarring, salivary duct damage): measured by specific questions
- Maternal anxiety or depression as indicated by the anxiety and depression dimension of EQ-5D-5L
 Maternal health-related quality of life: as elicited by the EQ-5D-5L
- Maternal and infant NHS healthcare resource use: collected on general practice visits and hospital admissions

9.6.4. 6 month follow-up

The following data will be collected using maternal self-report (via web-link to data capture platform, telephone, email or post) when the infant is 6 months of age:

 Any breastmilk feeding at 6 months according to maternal self-report: defined as any breastmilk feeding in the 24 hours prior to the infant reaching six months of age

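### The 3-month collection list in Protocol 9.6.3 counts support contacts from a different start point than the defined outcome, and leaves out the primary outcome item

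*Protocol*

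**What the plan says.** **Support used.** Section 6 defines this secondary outcome as the total of contacts, in person or by telephone, "with any breastfeeding supporter since the FROSTTIE procedure". The synopsis uses the same start point. The 3-month list in section 9.6.3 instead has "Total number of contacts with any breastfeeding supporter since first referral and specific means of support used". Section 9.5 separately records "Pre-trial entry breastfeeding support received" at baseline.

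**Primary outcome.** Section 6 gives it as "Any breastmilk feeding at 3 months according to maternal self-report", tied to the 24 hours before the infant turns three months old. The synopsis and flow chart agree. Section 9.6.3 lists exclusive breastmilk feeding, exclusive direct breastfeeding, the age at which breastmilk was last given and the time spent breastfeeding, but no item on any breastmilk feeding. Section 9.6.4 does list the later counterpart, "Any breastmilk feeding at 6 months according to maternal self-report".

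**Timing.** Section 7 describes the participant pathway as "routine post-intervention follow-up visit, 3 and 6 month post-intervention follow-up". The outcome definitions, sections 9.6.3 and 9.6.4, and Appendix A all use the infant's age.

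**The concern.** Section 9.6.3 is the protocol's own statement of what is collected at the primary time point, and a questionnaire can be expected to be built from it. An analysis plan can decide how to handle the data, but it cannot recover a question that was not put or reliably split a count that was started too early.

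If the list is followed literally, the support outcome that is analysed would include contacts made before the infant entered the trial. The primary endpoint would have to be pieced together from items designed for other outcomes.

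**Working it through.** No figure in the protocol needs to be reproduced here. The check compares each definition with the item meant to supply it.

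**1. Start point for support contacts**

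- Defined start: the procedure (synopsis and section 6, in agreement).
- Collected start: first referral (section 9.6.3).
- What lies between: referral comes before screening, consent, randomisation and the procedure. Section 9.2 says that after referral "mothers will receive advice on positioning and attachment", so most mothers should have at least one contact that falls inside one count and outside the other.
- Can the difference be removed? Section 9.5 collects pre-entry support, but gives no unit and no rule for subtracting it. Appendix A lets baseline data be taken at either the baseline or the intervention visit and allows up to 7 days to the intervention. Where baseline data are taken first, contacts in that interval may be missing from the baseline record yet included in the 3-month total.

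Effect on the comparison: Appendix A places randomisation at the intervention visit, so contacts before the procedure are essentially contacts before allocation. Let mean post-procedure contacts be m1 and m0 in the two arms. Let c > 0 be the mean number of earlier contacts, equal in both arms in expectation.

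- Difference in means: (m1 + c) − (m0 + c) = m1 − m0, unchanged.
- Ratio of means: (m1 + c)/(m0 + c) lies between m1/m0 and 1, so it is diluted.
- Variance: Var(pre + post) = Var(post) + Var(pre) + 2 Cov(pre, post). This exceeds Var(post) unless the covariance is below −Var(pre)/2, so precision is lost unless early and later contacts are clearly negatively related.

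Section 12.2 also allows a median difference. Medians do not add, so that contrast need not stay exactly the same. With no true difference in later contacts, however, the balanced earlier contacts create no systematic difference.

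**2. Can the listed items supply the primary outcome?**

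| Feeding in the 24 hours before 3 months | Primary outcome | Exclusive breastmilk | Exclusive direct | Time breastfeeding above zero | Age at last breastmilk |
|---|---|---|---|---|---|
| Only at the breast | yes | yes | yes | yes | current age |
| Breastmilk only, some by bottle | yes | yes | no | depends on any direct feeds | current age |
| At the breast plus formula | yes | no | no | yes | current age |
| Expressed milk plus formula | yes | no | no | no, if only direct feeding counts | current age |
| Formula only | no | no | no | no | an earlier age |

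The two exclusive items fail for every mixed-fed infant. Time spent breastfeeding picks up those fed partly at the breast. For an infant given expressed milk plus formula, only age at last breastmilk separates the fourth row from the fifth. The protocol states neither how precisely that age is recorded nor a rule that turns it into the primary outcome.

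The windows can also differ. The exclusive-feeding and time items refer to the 24 hours before the response, while the primary outcome refers to the 24 hours before three months of age. Section 13.2 provides telephone completion for delayed responses. An infant who stops breastmilk between three months and a late reply is a yes on the primary definition and a no on those items.

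**3. Timing phrase**

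Section 7 alone counts months from the intervention. The synopsis, flow chart, section 6, sections 9.6.3 and 9.6.4 and the Appendix A column headings all count from birth.

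**The case against.** The strongest reply is that section 9.6.3 is a list in a protocol and not the questionnaire, which is not among the documents. The primary outcome is defined consistently in three places as maternal self-report, and sections 7 and 13.2 say that primary outcome data will be collected that way. The age-at-last-breastmilk item is meant to establish whether, as well as when, an infant moved to formula alone. For an infant still receiving breastmilk, that is close to current status and not distant recall. This stands: a reader might infer from the omission that the primary endpoint will not be asked, or can be had only from a recalled age, and the documents support neither reading. What remains is that the main list for the primary time point lacks its principal item while the 6-month list has it.

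On support contacts, the baseline item might allow subtraction or adjustment. That is possible, but no unit or rule is given. A reader might also suppose that the early start biases the comparison. It does not bias a difference in means, because the added contacts precede allocation. Nor can a percentage loss of precision be given: it would need the variances of early and later contacts and their correlation, and the protocol has none of these.

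On timing, a reader might take section 7 as a competing endpoint definition that moves the assessment by the infant's age at intervention. Every section that defines or schedules an outcome uses age, so section 7 is loose wording in a summary sentence.

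**Conclusion.** The concern holds as a mismatch between collection and definition, in two parts.

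First, the support total in 9.6.3 is not the outcome defined in the synopsis and section 6. Balance of pre-allocation contacts follows from randomisation. On that basis the consequences are a count that is not the defined outcome, dilution of any ratio measure and, unless early and later contacts are clearly negatively related, reduced precision. One secondary outcome is affected, by an amount the protocol does not allow to be calculated.

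Second, the primary outcome item is absent from 9.6.3, and the items that are listed recover it only partly. The weak points are infants given expressed milk plus formula and mothers who respond late. How far this matters depends on the actual questionnaire. If that already asks the primary question, the defect is confined to the protocol text.

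The textual mismatches are certain; the practical consequences are conditional. Correction is worthwhile because the second part touches the primary endpoint. The section 7 phrase is a clerical matter.

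**What to change.** - In section 9.6.3, replace the first-referral start point with the one in section 6, "with any breastfeeding supporter since the FROSTTIE procedure".
- In section 9.6.3, add the primary outcome as an item, in the wording of its section 6 definition and with the same 24-hour window before three months of age.
- Check the 3-month questionnaire against both items.
- As a minor wording correction, restate the 3- and 6-month follow-up in section 7 by the infant's age.

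The cost is three wording changes in the protocol and one check of the questionnaire, which needs amending only if it shows the same gaps. Design, sample size and visit schedule are unaffected.
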